## 2. Specific Aims and Objectives

**Aim 1.** To test the efficacy of a real-time, provider-based individuation intervention to improve the receipt of high-quality rheumatic disease care among Black and lower SES individuals. *Hypothesis 1: Black and lower SES patients of providers randomized to the individuation intervention will achieve higher quality metric scores compared to patients of providers without the intervention.*

To accomplish this, providers randomized to the intervention arm will be asked to determine a set of questions that will help them uncover several unique “facts” about their patients. For example, questions about their patients’ hobbies, their daily routine, their family members (e.g., grandchildren), pets, etc. The concept behind this is that understanding these aspects that make each of their patients unique will reduce provider reliance on stereotyping. Patients actively enrolled in this study participating in Aim 2 (audiorecorded encounters), as well as other patients seen by enrolled providers who meet inclusion criteria during the study period who did not opt out of Aim 2, will all be included in de-identified chart review to examine quality of care related outcomes of interest by provider study arm.

**Aim 2.** To determine the effect of the individuation intervention on provider-patient communication, adherence, provider trust and care satisfaction. *Hypothesis 2: Providers randomized to the individuation intervention will exhibit less implicit prejudice in their communication compared to providers in the control arm; patients in the intervention arm will report greater trust, satisfaction, and adherence.*

To accomplish this, the provider-patient encounter will be audiorecorded and then aspects of communication that have previously been associated with implicit bias (e.g., physician-to-patient talk time ratio, physician word use (number of first-person pronouns, and number of positive and negative emotion-related words, divided by all words in the interaction) and total length of interaction will be assessed. In addition, surveys will be administered regarding trust, adherence and satisfaction, which have also been previously associated with implicit bias in provider-patient communication.

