### **3. General Description of Study Design**

We will conduct a cluster-randomized controlled trial. The clusters are 20 rheumatologists at multisite BWH and MGH-affiliated clinics. Rheumatologists will be stratified by hospital and by gender and randomly assigned. Ten rheumatologists will be assigned to the intervention arm and ten to the control. Assessments will be conducted for 8-10 patients per rheumatologist (max 100 patients total in each arm, 200 total). Randomization will be stratified by BWH and MGH Rheumatology main campus hospitals (MGH or BWH/ Faulkner (FH)) and their rheumatology satellite clinic sites, and by provider gender (male or female). Study schema is included as an attachment.

In addition to the 200 SLE, osteoarthritis, and inflammatory arthritis patients including RA who will be studied directly, we also will examine the medical records of patients with inflammatory arthritis, osteoarthritis, or SLE in the practices of the enrolled providers seen during the same study period. In addition to the chart review of patients who meet the inclusion criteria of less than 2 visits in the past year, we will perform a secondary analysis of all patients who may have been seen greater than 2 times in the past year as we anticipate a spillover effect from the intervention and would like to study

this. Patients who were approached to participate in the audiorecorded component of the trial and declined will not be included in this medical record review. We will have no direct interaction with these patients. Most medical records we will review will be for patients of enrolled providers who we had no direct interaction with. The goal of this chart review component is to more broadly examine the impact of the intervention on the quality measures described in Table 1 below, beyond those individuals who will have their encounters audiorecorded. In addition to allowing for a larger sample size for analysis, it also will allow for analyses that may not be influenced by the act of recording an encounter (e.g., possibly, due to the recording, care may be somewhat different from other patients in each providers' practice and this will allow us to capture both). For quality metrics that would only be a onetime screen or once every few years, we will review prior records to see if they were eligible for those outcomes (such as receipt of vaccinations).

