### 2. Patients

**2A. Identification:** We will identify patients with systemic lupus erythematosus, osteoarthritis, and/or inflammatory arthritis including rheumatoid arthritis, who are scheduled to see the enrolled providers from BWH/FH and MGH rheumatology main hospital clinics and their rheumatology satellite clinic sites. We will do this using a variety of methods including RPDR, EDW and EPIC searches and chart review. We will exclude any individual who has opted out of research and not contact them. Searches will be conducted by research assistants and supervised by the PI and Co-Is.

**2B. Inclusion/Exclusion Criteria:** We will include male and female patients of the participating providers who are able to provide consent, English-speaking,  $\geq 18$  years old, Black or African American or insured by Medicaid/Mass Health (as a proxy for low socioeconomic status), have a diagnosis of SLE, osteoarthritis, or inflammatory arthritis

including RA (or referred to rheumatology because of high suspicion for these conditions), and have been seen  $\leq 2$  times in the past year by the provider. In the past two years, there were  $>7,400$  patients with systemic rheumatic conditions at BWH and  $>5,600$  at MGH; 15% were Black or insured by Medicaid at BWH, 12.4% at MGH. We will exclude patients from the audiorecorded component who are incarcerated or unable to consent. We will exclude any patient from our searches who has opted out of research. If a patient declines to participate in the trial, we will not include them in the medical record review cohort either. However, if a patient of an enrolled provider does not decline participation in the audiorecorded component or is not approached for the audiorecorded component and meets our inclusion criteria, they will be included in our medical record review, along with patients who consent for participation in the audiorecorded component.

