## 3. Chart reviews

We will examine the charts of patients with lupus, osteoarthritis, or inflammatory arthritis seen >1 time by enrolled providers in both the intervention and control arms during the 6 months following provider enrollment, beginning  $\geq 1$  month after the date the provider takes the IATs. As indicated above, we will not obtain informed consent for patients of consented providers who will not be audiotaped but whose charts will be reviewed. Patients who were reached and invited to participate in the audiotaped encounter and surveys and did not consent or opted out of participation when approached will not have their chart reviewed. Patients who were not approached, or who were sent letters but could not be reached by phone or in person and did not opt out and are seen during this time frame by providers who are part of this study, may have their charts reviewed. We plan to collect demographics, social determinants of health, comorbidities/diagnoses, quality metrics related to their rheumatic disease, lab results, preventive care use (including immunizations), healthcare utilization (including ED visits, hospitalizations, outpatient visits and appointment no shows), medication use (including use of contraception as a quality metric), and medication refill data over the 6 months following the date of the recorded encounter. We will also see if any of the individuation

statements (smart phrases) were used for patients not specifically enrolled in the intervention (spillover from practice changes by the provider).

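### The cohort for the primary quality score is stated inconsistently, and chart-review-only patients have no defined index visit

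*Combined protocol and SAP*

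**What the plan says.** Hypothesis 1 (Section 2) is that "Black and lower SES patients of providers randomized to the individuation intervention will achieve higher quality metric scores" compared with patients of providers without the intervention. The text under Aim 1 takes into chart review the recorded patients and "other patients seen by enrolled providers who meet inclusion criteria during the study period", leaving out those who opted out of Aim 2. Section 4, 2B lists the criteria, among them "Black or African American or insured by Medicaid/Mass Health (as a proxy for low socioeconomic status", a listed diagnosis and at most two visits to the provider in the past year. It says that a patient of an enrolled provider who has not declined, or was not approached, and "meets our inclusion criteria, they will be included in our medical record review".

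Three other places read differently.

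- Section 3 refers to "patients who meet the inclusion criteria of less than 2 visits in the past year" and adds a secondary analysis of "all patients who may have been seen greater than 2 times in the past year".
- Section 6, 3. Chart reviews takes patients with the diagnoses "seen >1 time by enrolled providers in both the intervention and control arms during the 6 months following provider enrollment", and states no race, insurance or prior-year visit limit.
- Section 6, 5. Outcomes, which defines the primary outcome, measures it in all patients with the diagnoses seen in the 6-month study period and makes the recorded patients a separate subgroup.

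Section 9 ties the power calculation and the GEE model to Aim 1 and the quality score. It does not say which patients enter the model.

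**The concern.** Two analysts could each follow this protocol and report different primary results. Two of the literal readings have consequences beyond untidy wording.

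If more than one visit in the window is required, chart-review-only patients are selected on something that happens after their provider was randomised and, at least in part, after they have met that provider. Completed visits and no-shows are themselves secondary outcomes compared between arms. The rule would also discard patients with a single visit, although the score needs only one appointment and the following 30 days.

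If all patients with the diagnoses are scored, most of the charts could belong to people whom Hypothesis 1 is not about.

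The time origin is also unsettled. The score is anchored to an unspecified appointment, the chart-review data to the recorded encounter, and healthcare utilisation to an undefined encounter of interest. A chart-review-only patient has no recorded encounter, and nothing says which appointment counts when there are several.

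**Working it through.** **The plan's own figure.** Inputs from Section 9: 10 providers per arm, difference 0.5 SD, two-sided alpha 0.05. Design effect = 1 + (m − 1) × ICC; effective n per arm = 10m / design effect; power = Φ(0.5 / √(2/n) − 1.96).

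- m = 8, ICC 0.02: design effect 1.14, effective n 80/1.14 = 70.2, power 84.2%.
- m = 10, ICC 0.05: design effect 1.45, effective n 100/1.45 = 69.0, power 83.6%.

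Both match the stated 84%, so the arithmetic is sound. The 8 or 10 patients per provider are the directly studied patients of Section 3, whose recorded encounters the outcome section treats as a subgroup. The power statement therefore does not settle which set is primary.

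**The definitions side by side.**

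| Place | Race or insurance limit | Visit rule | Decliners |
|---|---|---|---|
| Section 2, Aim 1 | Yes, through the inclusion criteria | Through the inclusion criteria | Out |
| Section 4, 2B | Yes | ≤2 in past year | Out |
| Section 3 | Only by reference to the inclusion criteria | <2 in past year; >2 is secondary | Out |
| Section 6, 3. Chart reviews | None stated | >1 in the 6 months | Out |
| Section 6, 5. Outcomes | None stated | Seen in the 6-month period | Not mentioned |
| Section 9 | Refers to Aim 1 only | None | Not mentioned |

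**Section 3.** With <2 in one set and >2 in the other, a patient with exactly 2 prior-year visits falls in neither, yet is eligible under Section 4, 2B and 2C. This is probably a slip.

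**Chart reviews.** The >1 rule counts visits in the study window, while the ≤2 rule counts visits in the past year. A patient can satisfy both, so the rules are different but not mutually exclusive. Recorded patients have their quality metrics collected under Section 6, 2. Patients, with no visit-count rule, so >1 bears on chart-review-only patients. Equal return rates in the two arms would not make this selection harmless: the same proportion can return in each arm while different kinds of patients make up that proportion, and the mean score among returners can then differ with no effect in the full cohort.

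**Outcomes.** Section 4, 2B gives the Black-or-Medicaid share as 15% at BWH and 12.4% at MGH, for all systemic rheumatic conditions. If that share p applied to the three diagnoses (an assumption), charts outside Hypothesis 1 would be 1 − 0.15 = 85% to 1 − 0.124 = 87.6%, before any visit limit. If other patients gain a fraction r of the benefit in target patients, the average effect is p + (1 − p)r times the target effect. At r = 1 there is no dilution; at r = 0 the average is 12.4-15% of the target effect. The documents give no value for r.

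**The case against.** The strongest reply is that the primary set can be traced. Section 9 says the model is for Aim 1, Aim 1 refers to patients who meet the inclusion criteria, and Section 4, 2B repeats that record review requires them. In the outcome section, all patients is set against a recorded subgroup, so it may mean recorded or not rather than any race or insurance. The chart-review section later speaks only of patients seen in the time frame, which suggests that >1 was meant as at least 1. The 2-visit gap in Section 3 also looks like a slip, since >2 is the natural complement of ≤2.

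Much of this stands, and it is the likeliest intention. But neither the chart-review nor the outcome section says that eligibility carries over. Section 3 also offers a reason for casting wide, "In addition to allowing for a larger sample size for analysis", together with an interest in spillover, so a deliberately broad set is not excluded. The missing index visit remains under any reading of the cohort.

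A reader might go further and infer that a particular share of patients would be lost because next visits may be 4-6 months away. The documents do not support that: the remark in Section 5 concerns patients who could not be consented before their appointment, and it is not an average visit interval for the chart-review cohort. A reader might also infer that power collapses in an all-comers analysis. That would need the benefit in other patients, the number of charts per provider and the ICC in that wider population, none of which is given.

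**Conclusion.** The inconsistency is established from the text: the chart-review and outcome sections do not match the eligible cohort of Aim 1 and Section 4, 2B, and Section 9 does not name the set. The eligible cohort is a reasonable inference, so it would overstate the case to say that the plan has no primary population or has adopted an all-comers one.

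The consequences are conditional on a literal reading. Under the >1 rule, the size and direction of any bias cannot be derived from the documents; if at least 1 was meant, the return-visit selection disappears. Under the all-patients wording, about 85-88% of charts could lie outside Hypothesis 1, provided the share quoted for all systemic rheumatic conditions carries over to the three diagnoses. Dilution then ranges from none to severe according to how far other patients benefit. This should be fixed before outcome data are compared between arms.

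**What to change.** - **Section 9:** name the primary set as patients meeting the Section 4, 2B criteria, with at least one visit to an enrolled provider in the window, recorded or not, except decliners. Define it by citation, because a partial list would create yet another version of the cohort. State which consent-related criteria apply to patients whose charts are reviewed without consent.
- **Section 6, 3. Chart reviews and 5. Outcomes:** refer to that same set. In the former, replace more than one visit with at least one.
- **Section 3:** replace fewer than 2 prior-year visits with ≤2.
- **Index visit:** define one for every patient, for example the first eligible visit in the window, and use it for the 30-day score, the 6-month chart data and healthcare utilisation.
- **Other sets:** label any all-comers analysis as secondary.

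The cost is wording, plus some extra abstraction for single-visit patients. No new enrolment is needed. If the investigators did intend all comers as the primary set, that analysis becomes secondary and its larger sample no longer serves the primary test.

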#### 4. Return of results

For providers, all data will be deidentified and analyzed in aggregate. Unique de-identified codes will be used for the provider IATs that will be linked with the provider-patient recordings. The PI and Co-Is will be blinded and only see de-identified data which will be used for analyses. This is to reduce any risk to the providers reputation or employment. One experienced, trained research assistant will be able to link the data to identifiers should an unexpected situation arise and make this necessary however the PI and Co-Is will be blinded in order to ensure that the reputation of providers in their practices is preserved. Results in aggregate will be presented in an end-of-study Grand Rounds to both the BWH and MGH rheumatology divisions (there is a combined grand rounds). The title of this grand round will be “Presentation of Findings from Breaking Implicit Bias Habits Intervention Study.” We will submit this presentation to the IRB for approval prior to the Grand Rounds. If we do find examples of implicit bias and explicit discrimination, we will work with MGB equity leadership in this area, who are aware of this study and have been part of these discussions (including [name], [name] and [name]) to determine the best Division-wide training tools to use to address this need.

For patients, data will also be de-identified for analyses and de-identified codes will link survey responses with the provider-patient encounter. However, we will be able to link survey scores back to patients and after the completion of the 3-month adherence study, we will provide them with a score report indicating what their scores on each of the respective surveys mean. A sample score report will be submitted as an amendment once we have analyzed surveys and have determined the best way to present these data.

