## 2. Patients

Patients who consent to participate will be asked to have one clinical encounter with their provider recorded (preferably the next appointment) and then to complete a set of baseline surveys following that encounter including demographics, social determinants of health, everyday discrimination experiences, satisfaction with care, patient trust in the medical profession, patient perception of care centeredness and medication adherence. Surveys can be completed either via REDCaps via a link sent securely to the patient, or on paper forms (and then will be entered into REDCap by our study team). We will also assess medication adherence again 3 months after the encounter using a survey or a brief phone call, and over the 6-month period using the proportion of days covered data now available in the EMR. Patients will receive a \$30 gift card or e-check once the surveys are completed. We will also collect data from the patients' charts. These data include: demographics, social determinants of health, comorbidities/diagnoses, quality metrics related to their rheumatic disease, lab results, preventive care use (including immunizations), healthcare utilization (including ED visits, hospitalizations, outpatient visits and appointment no shows), medication use (including use of contraception as a quality metric), and medication refill data (proportion of days covered, available in the EMR) over the 6 months following the date of the recorded encounter. We will review the note from the date of the encounter and determine whether the individuation statement was documented in the intervention group.

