#### Secondary outcomes:

- 1) Change in provider IAT scores pre and post intervention. [name] at VCU will participate in this. She will submit to VCU for IRB approval for participation using completely deidentified data. A Data Use Agreement is in process between the two institutions.
- 2) Differences in perception of patient centeredness, patient satisfaction, patient trust in the medical profession, experiences of discrimination and adherence (at time of visit and at 3 months) comparing the intervention to non-intervention group. This secondary outcome is only for that patients enrolled in the study (not the chart review-only non-interaction group). We will additionally measure adherence for a full 6 month period using the proportion of days covered measure now available through the EMR both for participants in the survey component and for the chart review patients.
- 3) Healthcare utilization – we will compare ED visits, hospitalizations, outpatient visits completed and outpatient visit no shows between the two arms in the 6 months following the encounter of interest. We will include chart review patients (non-interaction) as well as patients who consented and had audiorecorded encounters in this part.
- 4) Provider communication (measured only for patients enrolled in the study who had their appointment audiorecorded). Provider communication will be measured using the recorded transcripts and compared between arms: a) physician-to-patient talk time ratio, b) physician word use (number of first person pronouns, and number of positive and negative emotion-related words, divided by all words in the interaction) and c) total length of interaction. This part of the study will be led by [name] (VCU). [name] will have a Data Use Agreement to receive de-identified transcripts for this analysis and separate IRB approval through her institution to work with these deidentified qualitative data.

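### Survey score reports, including adherence scores, may reach enrolled patients before their 6-month adherence and utilisation windows close

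*Combined protocol and SAP*

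**What the plan says.** Under Return of results in Section 6, the plan promises enrolled patients individual feedback: "after the completion of the 3-month adherence study, we will provide them with a score report". The content of that report is described as "indicating what their scores on each of the respective surveys mean". The promise is not limited to one arm. The next sentence adds that "A sample score report will be submitted as an amendment once we have analyzed surveys", so the format depends on survey analysis and an amendment.

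The surveys are listed in Section 6, Patients. They follow the recorded visit and include discrimination experiences as well as "satisfaction with care, patient trust in the medical profession, patient perception of care centeredness and medication adherence". Adherence is then self-reported once more: "We will also assess medication adherence again 3 months after the encounter using a survey or a brief phone call".

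Two sets of outcomes run beyond that point. Adherence is also measured "over the 6-month period using the proportion of days covered data now available in the EMR", and the secondary outcomes apply this measure "both for participants in the survey component and for the chart review patients". Utilisation compares emergency visits, hospitalisations, "outpatient visits completed and outpatient visit no shows between the two arms in the 6 months following the encounter of interest", again with chart-review patients included.

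No section holds the report until month 6, and Section 9 (Statistical Analysis) does not mention it.

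**The concern.** Telling patients what their adherence score means may change how they take or refill medication, and feedback on trust or discrimination may affect whether they attend. If this happens while refills and visits are still being counted, the last part of the 6-month outcome reflects the individuation intervention plus a second exposure that only surveyed patients receive.

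Both arms get the report, but its content is each patient's own scores. Hypothesis 2 predicts higher trust, satisfaction and adherence in the intervention arm. If that is right, control patients will on average receive less favourable reports. If less favourable reports prompt more correction, the contrast narrows.

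At stake are the interpretability of two secondary outcomes and the comparability of surveyed and chart-review-only patients within them.

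**Working it through.** **Plan's own figures.** The plan gives no power or effect size for PDC or utilisation. Its only power figure is for the quality score. With 8 patients per provider and ICC 0.02, the design effect is 1 + 7 × 0.02 = 1.14 and the effective n per arm is 80/1.14 = 70.2. Power for 0.5 SD is Φ(0.5·√(70.2/2) − 1.96) = 84.2%. With 10 patients and ICC 0.05, the design effect is 1.45, the effective n is 69.0 and power is 83.6%. Both match the stated 84%, but that outcome closes within 30 days and is not at issue here.

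**Inputs for the timing check.**
- Outcome window: 6 months from the encounter (Section 6, Patients and Secondary outcomes).
- Self-reported adherence follow-up: 3 months (Section 6, Patients).
- Recruitment: estimated at 6 months (Section 6, Providers).
- Assumed: patients enter uniformly over those 6 months, and the arm difference accrues evenly over the window.

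**Exposure.** A patient entering at calendar month t has a window from t to t + 6. If the report goes out at time R, the exposed time is max(0, t + 6 − R).
- Per patient at month 3: R = t + 3, so every patient has 3 exposed months, and 3/6 = 50%.
- When the last patient reaches month 3: R = 6 + 3 = 9, so exposure is max(0, t − 3). Half the patients are exposed. The mean is (1/6)·∫₃⁶(t − 3)dt = 4.5/6 = 0.75 months, and 0.75/6 = 12.5%.
- Calendar month 10: the mean is (1/6)·∫₄⁶(t − 4)dt = 2/6 = 0.33 months, or 5.6%.
- Calendar month 12 or later: the last window has closed, so 0%.

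**Attenuation.** If a share f of the arm difference is lost after the report and s is the exposed share, the 6-month difference becomes Δ(1 − f·s). The documents give no value for f; 25–100% is an assumed range.

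| Release | Patients exposed | Mean months | s | Loss f·s |
|---|---|---|---|---|
| Per patient, month 3 | 100% | 3 | 50% | 12.5–50% |
| Calendar month 9 | 50% | 0.75 | 12.5% | 3.1–12.5% |
| Calendar month 10 | 33% | 0.33 | 5.6% | 1.4–5.6% |
| Calendar month 12 or later | 0% | 0 | 0% | none |

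**Pooled analysis.** If enrolled patients are a fraction p of those analysed, with equal weight per patient and the same underlying difference in both subsets, the loss is p·f·s. The plan does not give p. Section 3 says that most reviewed records will belong to patients with no direct study contact, which implies p < 0.5. The loss is then below 6.25–25% on the first row and below 1.6–6.25% on the second.

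**Equal versus unequal response.** Suppose the report raised PDC by an assumed 2–10 percentage points after receipt in both arms. At s = 50%, 6-month PDC would rise by 1–5 points in each arm, and the difference would not change. An assumed 2–5 point gap in response between arms would shift the difference by at most 1–2.5 points at s = 50%, or 0.25–0.625 points at s = 12.5%.

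**The case against.** A reader might infer that every enrolled patient gets feedback exactly halfway through follow-up, and that 12.5–50% is the expected loss. The documents do not support this. The trigger is completion of the 3-month adherence study, which may well be a study-wide milestone, and the report's format waits for survey analysis and an amendment. Release per patient at month 3 is the earliest reading, and on the latest readings exposure is small or nil.

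A reader might also infer that the report biases the arm comparison by its mere presence. It does not: both arms receive it, and an equal response cancels. The range for f assumes a loss rather than demonstrating one. A differential response is plausible if scores differ by arm, but nothing in the documents establishes its size or direction.

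Nor does the mixing of surveyed and chart-review patients arise mainly from the report. Consent, recording and surveys already separate the groups, and Section 3 uses chart review partly to look beyond the effect of recording. Mixing that occurs in both arms is heterogeneity, not bias in itself.

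These points limit the size but do not remove the issue. The stated rule still permits feedback on a measured behaviour during follow-up. Under a study-wide release before calendar month 12, exposure would also depend on enrolment date. For visit outcomes, the share of time may understate the share of events: Section 5 notes that a patient's next visit may be 4–6 months away, which is after a month-3 report.

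**Conclusion.** The point holds as a timing gap affecting secondary outcomes. The plan allows individual score reports, including adherence, to reach enrolled patients in both arms before their 6-month PDC and utilisation windows close, and it neither fixes the release date nor provides for it in the analysis.

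The size depends on a trigger that the plan leaves open, from half of the window down to none. The corresponding losses rest on uniform accrual, an evenly accruing arm difference, an assumed f and a response that differs by arm. They apply to enrolled patients only and shrink when chart-review-only patients are pooled in.

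It would be wrong to extend the concern to the main results. The 30-day primary outcome, the recorded communication, the post-visit surveys and the 3-month self-reported adherence all precede the report on any reading.

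**What to change.** In Section 6, Return of results, replace the present release condition with: 'after that patient's own 6-month follow-up window has closed'. Naming the patient's own window also settles whether the trigger is individual or study-wide.

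This is a one-clause edit that can go into the amendment already planned for the sample report. It needs no extra data or patients. The cost is that patients wait up to about 3 months longer for their report.

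If earlier release is kept, record each patient's release date and add a sensitivity analysis of PDC and utilisation restricted to months 0–3.
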